4.2 Data Collection Summary

Subjects will have undergone a decompression surgery with the coflex® Interlaminar Technology, 1 or 2 level decompression with or without fusion according to the physician's standard procedures. Table 1 describes the anticipated time points which will be collected as part of the retrospective data review. Please see Section 4.4, Data Collection Procedures for additional details regarding the data points intended to be captured at the designated time points.

	Baseline	Surgical Treatment	Post-Operative Hospital Stay	Follow-Up Visit(s)
Demographics & Risk Factors	X			
Prior Surgery Detail (If available)	X			
Diagnosis	X			
Operative Summary		X		
Procedure Payer Information		X		
Secondary Treatments			X	X
Complications		X	X	X
Work Status / ADL (If available)	X		X	X
Patient Questionnaires (If available)	X	X	X	X
Diagnostic Imaging History	X	X	X	X

4.3 Informed Consent

A waiver of informed consent will be requested from the IRB for all subjects as this study is collecting retrospective data. As indicated above, the study is a review of medical records that poses no risk to the patients and minimal risk to loss of patient privacy. All individual information used in the study will be de-identified and, if published or presented publicly, the information will be disclosed in aggregate with no links or identifiers to individual subjects.

4.4 Data Collection Procedures

Site staff or a Paradigm Spine representative will review and evaluate medical charts for enrollment into the study based on the inclusion/exclusion criteria. All people involved with the collection or analysis of the data will be familiar with HIPAA requirements for handling Protected Health Information (PHI). For purposes of de-identification, eligible patients (subjects) will be given a unique subject identification number that will help to protect their privacy in the study records. The research team will not capture any patient-specific identifiers such as date of birth or initials in the study records. Data will be entered into CRF's and then sent to the biostatisticians for analysis.

The following data points will be captured at the designated time points.

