Study Design	Retrospective, multi-center, post-market clinical study
Devices	coflex® Interlaminar Technology
Data Collection	Clinical, radiologic and patient reported outcomes data will be collected for approximately 5000 patients from 50 sites
Study Duration	Up to 6 months for data collection Start Date: June 2013 End Date: April 2017
Study Objectives	
Primary Objective:
 
• To assess the operative details and safety outcomes associated with the use of the coflex device• To assess post-operative adverse events• To assess post-operative follow-up duration 
Secondary Objectives:
 
• To measure and compare patient reported outcomes (e.g., VAS, Patient Satisfaction and ODI) at baseline and final follow-up• To measure and compare clinical and radiologic outcomes at baseline and final follow-up• To measure and compare the clinical, radiologic, and patient reported outcomes at interim follow-up visits• To assess the impact of demographics and risk factors on clinical, radiologic, and patient reported outcomes•
Inclusion Criteria	Patients must meet the criteria specified in the device labeling including radiographic confirmation of at least moderate lumbar stenosis, which narrows the central spinal canal at one or two contiguous levels from L1-L5 that require surgical decompression.
Exclusion Criteria	There are no exclusion criteria's for this study.

Risk/Benefit Assessment

The study is a retrospective analysis of medical records that poses no risk to the patients and minimal risk to loss of patient privacy. All results will be de-identified in the process of data review. There are no benefits to the subject as this data is being collected to obtain additional clinical evidence to support publications and marketing.

Study Abbreviations

Abbreviation	Definition
BMI	Body Mass Index
FDA	Food and Drug Administration
GCP	Good Clinical Practice
HIPAA	Health Insurance Portability and Accountability Act of 1996
ICH	International Committee on Harmonization
IRB	Institutional Review Board
MRI	Magnetic Resonance Imaging
CT	Computed Tomography
DEXA	Dual Energy X-ray Absorptiometry

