1.0 Introduction

The coflex® Interlaminar Technology - manufactured by Paradigm Spine - is intended for use as a permanent implant between the lamina of 1 or 2 lumbar motion segments in the treatment of moderate to severe lumbar spinal stenosis. The device is specifically designed to provide stabilization without fusion in cases of stenosis with or without facet joint hypertrophy, subarticular recess stenosis or foraminal stenosis. It is restricted for use to one or two levels in the region of L1 – L5.

The height of the neuroforamen is maintained and the facet joints will be relieved. By this a further destruction is prevented. Unlike conventional stabilization methods as for example spinal fusion, the function of the segment will be maintained and adjacent structures will be effectively protected.

Possible risks, which could occur after implantation of the coflex® Interlaminar Technology are breakage of the implant, displacement of the implant, pain which is caused by the implant, infections, bleedings and hematoma. The benefit of the study lies in the fact that first-time retrospective data is raised for potential improvement regarding therapy of lumbar back pain with the treatment of the lumbar spinal stenosis, which, in the future, can lead to an improvement of the therapy.

In this study, Paradigm Spine will retrospectively collect clinical and radiographic data for patients treated with the coflex® Interlaminar Technology during normal conditions of use. This data will provide evidence to support publications and marketing.

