3.0 Eligibility Criteria

3.1 Inclusion criteria

Patient considered for enrollment in this study must meet all of the following inclusion criteria:

- Patients must meet the criteria specified in the device labeling including radiographic confirmation of at least moderate lumbar stenosis, which narrows the central spinal canal at one or two contiguous levels from L1-L5 that require surgical decompression.

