3.2 Exclusion criteria

There are no exclusion criteria for this study.

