4.0 Study Design

This is a retrospective, multi-center, post-market study collecting clinical, radiographic, and patient reported outcomes for subjects who have been treated 1 or 2 levels with the coflex® Interlaminar Technology or decompression with or without fusion.

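### The protocol does not say how eligible charts are sampled or accounted for, so it permits entry related to outcomes already on record

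*Combined protocol and SAP*

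**What the plan says.** - **Timing.** Section 4.0: "This is a retrospective, multi-center, post-market study collecting clinical, radiographic, and patient reported outcomes for subjects who have been treated 1 or 2 levels". Section 4.2: "Subjects will have undergone a decompression surgery with the coflex® Interlaminar Technology, 1 or 2 level decompression with or without fusion". Surgery, and whatever follow-up is on record, precede enrolment.
- **Who selects.** Section 4.4: "Site staff or a Paradigm Spine representative will review and evaluate medical charts for enrollment into the study based on the inclusion/exclusion criteria". Nothing limits the selector to pre-operative records or keeps treatment or outcome from view.
- **Who is eligible.** Section 3.1: "Patients must meet the criteria specified in the device labeling including radiographic confirmation of at least moderate lumbar stenosis", at one or two contiguous lumbar levels needing decompression. Section 3.2: "There are no exclusion criteria for this study".
- **How many.** The Protocol Summary foresees "approximately 5000 patients from 50 sites", an average of 5000/50 = 100 per site. It gives no split by procedure and no per-site quota or cap.
- **Nearest text to a complete-entry rule.** Section 4.4: "eligible patients (subjects) will be given a unique subject identification number that will help to protect their privacy in the study records". The sentence opens by giving de-identification as its purpose.
- **Dates.** The Protocol Summary gives June 2013 to April 2017 as study duration, next to a data-collection period of at most 6 months. Neither is tied to date of surgery.
- **What the records hold.** Section 4.4.2 collects repeat surgery and its reason. Section 4.4.4 collects complications, secondary treatments and, where available, VAS, ODI and satisfaction.
- **What is analysed.** Section 5.2 makes follow-up duration and the incidence of secondary surgery the primary endpoint.

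**The concern.** Eligibility criteria settle who may enter a chart review. They do not settle that everyone who qualifies does enter. In a prospective study this matters less, because nobody knows the outcome at enrolment. Here the person opening the chart may be able to see whether the patient was reoperated, how long follow-up lasted and which procedure was done, and that person may work for the sponsor.

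Selection need not be deliberate. Section 5.3 says clinical outcome measures are collected only where they exist, so a natural preference for well-documented charts would favour patients with more follow-up. Follow-up duration is itself part of the primary endpoint.

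If entry depends on outcome, a larger sample only narrows the interval around a biased value. Covariate adjustment cannot repair it when entry probabilities are unrecorded. Without a log, no reader of the results could tell whether it had happened.

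**Working it through.** **No planned figure to reproduce.** The 5000 comes without a power statement, effect size, event rate or allocation. The rates, selection ratios and group sizes below are assumptions that show scale only.

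**Effect on one group's incidence.** Let p be the true reoperation rate and r the probability that a reoperated chart is entered, relative to one without reoperation. Then

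observed rate = p·r / (p·r + 1 − p).

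At p = 12%:
- r = 0.9: 0.108/0.988 = 10.9%
- r = 0.8: 0.096/0.976 = 9.8%
- r = 0.5: 0.060/0.940 = 6.4%

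At r = 0.8 with every other chart entered, 0.12 × 0.2 = 2.4% of the group's eligible charts are left out, or two to three in every 100.

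**Effect on a between-group difference.** Suppose the true rates are equal and r = 0.8 in one group only. Then SE = √[p(1 − p)(1/n₁ + 1/n₂)].

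| True rate | Group sizes | Observed rate | Spurious difference (points) | SE (points) | Difference / SE |
|---|---|---|---|---|---|
| 8% | 2500 / 2500 | 0.064/0.984 = 6.5% | 1.50 | 0.77 | 1.95 |
| 12% | 2500 / 2500 | 0.096/0.976 = 9.8% | 2.16 | 0.92 | 2.35 |
| 15% | 2500 / 2500 | 0.120/0.970 = 12.4% | 2.63 | 1.01 | 2.60 |
| 12% | 1667 / 1667 | 9.8% | 2.16 | 1.13 | 1.92 |
| 12% | 1000 / 4000 | 9.8% | 2.16 | 1.15 | 1.88 |

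**Chance of a false significant difference.** This uses a normal-approximation two-proportion test at two-sided 0.05. Section 5.1 does not state sidedness, and its Fisher's exact test is slightly more conservative. At p = 10% and r = 0.8 in the coflex group only, the chance is 62% with 2500 per group and 42% with 1000 coflex and 4000 comparator. Over true rates of 5% to 20% it runs from 37% to 86% and from 23% to 67% respectively.

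**Equal selection.** The observed odds are r·p/(1 − p). If r is the same in both groups it cancels, and the odds ratio is unchanged. Each group's incidence is still wrong.

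**With complete entry.** r = 1, so the observed rate equals the true rate and the false-positive chance from this source returns to 5%.

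**The case against.** The best defence is that Section 4.4 ties chart review to the criteria, that the criterion spelled out in Section 3.1 is pre-operative, and that with no exclusion criteria the plan names no ground for omitting an eligible chart. Section 4.4 also treats eligible patients and subjects as the same people. On that reading, every eligible chart enters. The reading is possible, but neither text requires it: one widens eligibility and the other concerns de-identification. If complete entry is meant, one sentence would say so.

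The June 2013 to April 2017 span is much longer than 6 months and could be the intended record period. The Protocol Summary does not say so, and a window alone would not compel complete capture.

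A reader might go further than the text in four ways, and the defence is right to resist each:
- **That charts are being picked on outcome.** Nothing says so. The plan leaves it possible. The stated purpose, "This data will provide evidence to support publications and marketing", is context and not evidence of a sampling defect.
- **That sites stop at a number.** The target is approximate and may be a forecast of volume.
- **That every result is biased.** An odds ratio survives selection that is equal across procedures. Section 5.2 also frames the primary endpoint around coflex, and no between-group test of reoperation is set out, although the title is comparative.
- **That a 20% selection gap always exceeds two standard errors.** It does not at 8% with 2500 per group, nor at 12% with either of the other two allocations shown.

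**Conclusion.** The point stands as a gap in the design. Sites could follow this protocol exactly and still enter an outcome-related sample, and no later analysis could detect or correct it. The exposed quantities are the incidence of secondary surgery and the follow-up duration. Comparisons between procedures are exposed only if selection differs by procedure, which nothing in the plan prevents.

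Under the assumed inputs, a 20% relative deficit in entry of reoperated charts lowers the reported incidence by 1.5 to 2.6 points. Confined to one group, that is roughly 1.9 to 2.6 standard errors, depending on the assumed rate and allocation. These figures show that modest selection would matter at this sample size. They do not estimate what will occur.

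**What to change.** Amend Section 4.4 as follows:

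1. At each site, before any follow-up record is opened, list every patient who had one of the index procedures within a fixed index-surgery window, using operating-room or billing records. State whether the Protocol Summary dates are that window.
2. Judge eligibility from pre-operative and index-operative records only, preferably by someone without access to follow-up.
3. Enter all eligible patients. If a site must cap, take patients consecutively from the start of the window or by random draw.
4. Keep and report a log by procedure of numbers listed, eligible and entered, with reasons for non-entry.

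The cost is a protocol amendment, which under Section 6.1 needs local or central IRB and sponsor approval before data collection, plus one procedure list and one log at each of about 50 sites. Sites lose the freedom to submit convenient charts, and some entered charts will have sparse data. The change deals only with selection at chart entry. Confounding by choice of treatment and missing questionnaires remain.

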4.4.1 Baseline Visit

- Diagnosis
 - Presenting symptoms
 - Documented failed conservative treatment
 - Patient reported outcome questionnaires, if available
 - Prior treatment details
- Pre-Operative Demographics
 - Date of visit
 - Age
 - Gender
 - Race
 - Ethnicity
 - Work Status / ADL
 - Height (in)
 - Weight (lbs)
 - BMI

- Risk Factors
 - Tobacco Use
 - Alcohol Use
 - Comorbidities
 - Diabetes
 - Bone Density
 - Medications
- Diagnostic Imaging
 - MRI and CT of affected lumbar levels
 - Radiographs

4.4.2 Surgical Treatment Visit

- Operative Summary
 - Date of surgery
 - Surgical procedure
 - Operative time
 - Estimated blood loss
 - Anesthesia details
 - Treated level(s)
 - Device size
 - Intra-operative/early post-operative complications, such as:
 - Dural tears
 - Hematomas
 - Fractures
 - Nerve injury
 - Diagnostic imaging History
 - Dictated operative notes
- Repeat Surgery Summary
 - Date of surgery
 - Reason for surgery (reoperation, revision, removal, etc.)
 - Surgical procedure
 - Operative time
 - Estimated blood loss
 - Anesthesia details
 - Treated level(s)
 - Surgical intervention performed
 - Device size
 - Intra-operative/early post-operative complications

- Dural tears
- Hematomas
- Fractures
- Nerve injury
- Diagnostic imaging History

4.4.3 Post-Operative Hospital Stay

- Duration of hospital stay
- Post-operative complications and other observations from hospital stay
- Patient reported outcome questionnaires, if available
- Diagnostic Imaging
- Narcotics use

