2.0 Study Purpose

2.1 Primary Objective

- To assess the operative details and safety outcomes associated with the use of the coflex device
- To assess post-operative adverse events
- To assess post-operative follow-up duration

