4.4.4 Follow-Up Visits

The following longitudinal data will be collected for all follow-up clinic visits through final follow-up:

- Work status / ADL
- Compliance with postoperative protocol/restrictions (if applicable)
- VAS (as available)
- ODI (as available)
- Patient satisfaction (as available)
- Complications
- Secondary treatments
- Narcotics use
- Diagnostic Imaging
- Incidence of Epidural Steroid Injections (ESI)

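### Complications are recorded by setting, with no onset day, no common window after surgery and no readmission item, so their rates would cover unequal periods between procedures

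*Combined protocol and SAP*

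**What the plan says.** Section 2.1 lists among the primary objectives "To assess post-operative adverse events", with no period attached. Complications are then collected in three places, and the table in section 4.2 marks them in the same three columns:

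- **Surgical visit (4.4.2):** "Intra-operative/early post-operative complications, such as" dural tears, hematomas, fractures and nerve injury. How long "early" lasts is not stated.
- **Index hospital stay (4.4.3):** "Post-operative complications and other observations from hospital stay". The same section also collects "Duration of hospital stay".
- **After discharge (4.4.4):** "The following longitudinal data will be collected for all follow-up clinic visits through final follow-up". The items include complications, secondary treatments and epidural steroid injections. Neither visit days nor an end of follow-up are fixed.

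Section 4.4.2 also has a repeat-surgery summary with date, reason, procedure and complications. Section 5.3 says only that new or worsening complications will be summarized. It gives no window, denominator or breakdown by setting.

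**The concern.** The listed items date the index operation and any repeat operation, but not a complication. The hospital-stay item closes at discharge, so its length is the patient's own stay, which is itself recorded as data. The follow-up item runs to a last visit that also varies. If procedures differ in stay or in follow-up, complication rates cover different periods and part of any difference is exposure time rather than risk. Without an onset day, the counts may not be recoverable for a common window later.

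Readmissions and emergency visits are not named items. An event after discharge can therefore be lost if it neither reaches a clinic note nor leads to recorded repeat surgery.

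This matters because the study title sets coflex against decompression with or without fusion, adverse events are a primary objective, and the Introduction says the data will support publications and marketing.

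**Working it through.** The documents give no complication rate, no stay by procedure and no group sizes, so there is no planned figure to reproduce. The numbers below are illustrations on assumed inputs. The true risk is the same in both procedures throughout, so any gap is an artefact.

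**Assumptions.** Daily risk h = 1% (also 0.5%); stays of 1 and 4 days (also 1 and 2); 14-day horizon; 1500 patients per group; share m of post-discharge events that never reach the study record = 20% or 40%.

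**Step 1. Hospital-stay count alone.** Rate = 1 − (1 − h)^stay.

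- h = 1%, stay 1 day: 1.0%. Stay 4 days: 1 − 0.99^4 = 3.9%. Ratio 3.9; Fisher's exact p about 2e-7.
- h = 1%, stay 2 days: 1 − 0.99^2 = 2.0%. Ratio to the 1-day stay 2.0; p = 0.03.
- h = 0.5%: nearly the same ratios; p = 0.0004 for 1 versus 4 days and 0.21 for 1 versus 2 days.

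**Step 2. All settings pooled, which the collected items allow.** True 14-day rate T = 1 − 0.99^14 = 13.1%. Recorded rate = in-hospital rate + (T − in-hospital rate) × (1 − m). The spurious gap is therefore m × (difference in in-hospital rates).

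| Missed after discharge | 1-day stay | 4-day stay | Gap (points) | Ratio | Fisher p |
|---|---|---|---|---|---|
| 0% | 13.1% | 13.1% | 0 | 1.00 | 1.0 |
| 20% | 1.0 + 12.13 × 0.8 = 10.7% | 3.94 + 9.19 × 0.8 = 11.3% | 0.2 × 2.94 = 0.59 | 1.05 | 0.68 |
| 40% | 1.0 + 12.13 × 0.6 = 8.3% | 3.94 + 9.19 × 0.6 = 9.5% | 0.4 × 2.94 = 1.18 | 1.14 | 0.27 |

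At h = 0.5%, the pooled p-values are 0.81 (20% missed) and 0.48 (40% missed).

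**Step 3. A second event-time model.** Here both procedures have the same 30-day risk R of 5% or 10%. Event times are exponential with mean 5 or 15 days, truncated at day 30, or uniform over 30 days. Stays are 1 versus 3 or 2 versus 4 days. Recorded risk = R × [S + c × (1 − S)], where S is the share of events before discharge and c is the probability that a later event is captured.

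- Hospital stay alone (c = 0): ratios 1.67 to 3.0, gaps 0.33 to 2.71 points.
- Pooled, c = 0.8: gaps 0.07 to 0.54 points.
- Pooled, c = 0.5: gaps 0.17 to 1.35 points.
- Pooled, c = 1: no gap.

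Both models agree: the artefact is large for hospital-stay counts alone, modest for pooled counts with losses after discharge, and zero with full capture over a common window.

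**The case against.** A reader might infer that the procedure with the shorter stay is bound to look safer. The documents do not support that. It needs a difference in stay, and they give no stay by procedure. It also needs either a comparison of hospital-stay counts alone or incomplete capture after discharge. Section 5.3 plans only a summary, and the general Fisher's exact sentence in section 5.1 names neither hospital-stay complications nor procedure groups.

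A reader might also infer that events after discharge have nowhere to go, or that the most serious ones are lost. That is too strong. The cause of a readmission or emergency visit can be entered under complications or secondary treatments at a later clinic visit, and a reoperation has its own dated form. The source is the medical chart, so loss of an event in a patient who never returns is possible but not established. The secondary surgical interventions in section 5.2 are not tied to the hospital stay. The surgical-visit item for early complications has no stated cut-off at discharge either, so the early window is not simply the stay.

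These points limit the size and certainty of the bias, and they stand. They do not supply an onset day, a common window or a readmission item. The CRF is not among the documents; if it already holds an onset date for each complication, the first gap closes in practice, but the protocol should say so. Incomplete capture of care given elsewhere is a limit of any chart review, and a fixed window alone does not cure it.

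**Conclusion.** The point holds in a conditional form. For a primary objective, complications are collected over periods set by setting, stay and last visit. The items listed do not allow those periods to be made common. Rates by setting or over all follow-up are therefore not comparable between procedures if stay or follow-up differs, and some events after discharge can be missed.

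Neither the size nor the direction of any bias can be fixed from the documents. The ratio of 3.9 belongs only to a hospital-stay comparison that the plan does not specify. With settings pooled, the same assumptions give a gap of about 0.6 points with 20% of later events missed and 1.2 points with 40% missed. Neither is distinguishable from chance at 1500 per group. Recorded rates would also be too low overall, by roughly 2 to 5 points against 13.1%. The change is worth making before abstraction starts, because adding an onset day afterwards would mean rereading charts for about 5000 patients at 50 sites.

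**What to change.** - **Sections 4.4.2 to 4.4.4:** record the day after index surgery for every complication, abstracted from the whole available chart regardless of setting. Add one item for readmission or emergency visit (day, reason).
- **Section 5:** report complications and readmissions per procedure within prespecified windows from surgery, for example 0–30 and 0–90 days, with the number of patients observed through each window. State that hospital-stay-only rates will not be compared across procedures.
- **Limitation to state:** care given elsewhere and absent from the chart stays unseen.

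The cost is protocol wording, one day field and one CRF item. The charts are being read anyway. Abstraction takes slightly longer and reported complication rates will be somewhat higher.
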